8.7. Vital Signs

Summary statistics for vital signs will be presented at Screening, Baseline, Weeks 4, 26, 39, 52, 65, and 78.

The original protocol required triplicate measurements for blood pressure and HR. It was determined as a non-safety concern therefore this requirement was removed as part of a protocol amendment 6.0 dated 13 May 2021 to reduce burden on participants. Since up to triplicate measurements may have been collected, for descriptive statistics of actual values and changes from Baseline to each visit and assessment, multiple values around the same timepoint will be averaged.

Actual values and changes from Baseline to each visit and assessment will be summarized using descriptive statistics. The incidence of clinically significant abnormal values will be summarized for select vital signs using descriptive statistics.

Descriptive statistics for each orthostatic vital sign parameter (supine minus standing systolic blood pressure [SBP], and supine minus standing diastolic blood pressure [DBP]) at Baseline and over time will be presented by treatment group.

The incidence of orthostatic clinically significant abnormal values (defined in [Table 5](#)) will be summarized using descriptive statistics. Clinically relevant abnormalities will be summarized using two methods (a) the observed values and (b) both observed value and the change relative to Baseline.

A listing for clinically significant abnormal vital signs will be presented.

Table 5: Criteria to Determine Clinically Relevant Abnormalities in Vital Signs

Vital Sign	Observed Value	Change Relative to Baseline
Temperature	>38 °C	Increase of >1 °C
	<36 °C	
Heart rate	>100 beats per minute	Increase of >15 beats per minute
	<60 beats per minute	Decrease of >10 beats per minute
SBP	>160 mm Hg	
	>140 mm Hg	Increase of >15 mm Hg
	<90 mm Hg	Decrease of >15 mm Hg
DBP	>100 mm Hg	
	>90 mm Hg	Increase of >15 mm Hg
	<50 mm Hg	Decrease of >15 mm Hg
Body Weight		Increase of $\geq 7\%$
		Decrease of $\geq 7\%$
SBP Supine minus Standing	>20 mm Hg	
DBP Supine minus Standing	>10 mm Hg	

8.8. **Electrocardiography (ECG)**

8.8.1. **ECG Measures Handling and Time Points**

A single resting 12-lead ECG is conducted after at least 5 minutes of supine rest at Screening (Visit 0). If there is evidence of a prolonged QTcF interval at Screening (defined as a QTcF interval of >450 msec for men and >470 msec for women) then the ECG is repeated twice, and the mean of the 3 measurements will be used for the summary.

Planned timepoint ECG assessments are specified in the SoAs ([Table 1](#) and [Table 2](#)).

If the local ECG reading results at the site match any of the below Stopping Rules, the participant should stop taking study medication until the central ECG reader's report is received. If the central reader does not report a QTcF interval that would lead to discontinuation according to the above, then the participant should restart study medication.

Participants should be discontinued from study drug if any of the following QTcF Stopping Rules are met at any visit:

- QTcF >500 msec (based on any ECG administration)
- QTcF >480 msec with concurrent increase in QTcF >60 msec (Δ QTcF, based on the mean value from ECG administrations) from Baseline (Day 1)

If the local ECG reading results at the site meet the Monitoring Rule (QTcF >480 msec or Δ QTcF >60 msec), the participant can continue the study drug per protocol until the central ECG reader's report is received. If central reader confirms meeting a Monitoring Rule, the participant will stay on study drug (per protocol) and will return for a follow-up ECG after 3-14 days. If at the follow-up ECG, QTcF change is confirmed (meets Monitoring Rule) then the participant will be discontinued from study drug.

8.8.2. ECG Parameters Data Presentations

Change from Baseline values will be calculated for each participant and visit as the value at the visit (averaged if measurements are taken in triplicate as described above) subtracted by the average Baseline value.

ECG data summaries and listings will include the following:

- The numbers and percentages of participants with the following clinically potential significant values will be presented at Baseline and each post-baseline visit:
 - Absolute QTcF values >450 msec; >480 msec; >500 msec
 - Change from Baseline in QTcF >30 msec; >60 msec
 For HR, PR and QRS use below:
 - HR: decrease of HR from baseline >10 bpm resulting in HR <60 bpm
Increase of HR from baseline >15 bpm resulting in HR >100 bpm
 - PR: increase of PR from baseline >25% resulting in PR >200 ms
 - QRS: increase of QRS from baseline >25% resulting in QRS >100 ms

Data listing of these values together with Baseline value and change from Baseline will also be provided:

- The number of participants and percentages of ECG interpretation (Normal/Abnormal Not Clinically Significant, Abnormal Clinically Significant) as determined by the ECG Central Lab at each scheduled visit and time point as well as the shift table from Baseline to each post-baseline visit will be presented by treatment groups
- The number and % of participants with ECG alerts as determined by the ECG Central Lab will be presented by treatment groups
- Descriptive statistics and boxplots of quantitative 12-Lead ECG parameters (HR [bpm], QTcF [msec], QTcB [msec], QT [msec], PR [msec], QRS [msec] and RR [msec]) and changes from Baseline will be presented by scheduled visits, time point and treatment group
- Central ECG Review of abnormalities will be summarized.

8.9. Columbia-Suicide Severity Rating Scale (C-SSRS)

The C-SSRS will be used to rate the participant's degree of suicidal ideation on a scale ranging from "no suicidal ideation" to "active suicidal ideation with specific plan and intent". The C-SSRS Baseline version will be completed at Screening (Visit 0), while the C-SSRS Since Last Visit version will be completed as specified in the SoA ([Table 1](#) and [Table 2](#)).

Summary statistics for the C-SSRS at each visit will be presented by treatment group using observed data. The Baseline value will be based on the closest non-missing recency score prior to first dose of study drug.

The number of participants evaluated and the number and percentage of participants with any positive report of Suicidal Behavior, Suicidal Ideation, and Suicidal Behavior or Ideation at Baseline and post-baseline visits will be presented by treatment group. A positive report of Suicidal Behavior or Ideation is defined as a "yes" response on any ideation item (positive Suicidal Ideation), or a "yes" response to any behavior item (positive Suicidal Behavior). The shift from Baseline will be summarized by (a) worst post-baseline value (b) Last observed non-missing post-Baseline value and then (c) at each post baseline visit. .

C-SSRS assessment results for each participant at each visit will be listed by treatment group using observed data. Both lifetime and recency scores at Screening Visit will be listed.

8.10. Pregnancy Test

Serum/urine pregnancy test results will be listed for women of child-bearing potential only.

8.11. Physical and Neurological Examination

The physical (full and brief) and neurological examination results, graded as normal or abnormal (or for some neurological examinations other categories are used such as hypoactive, hyperactive, etc.), will be summarized using counts and percentages at visits described in [Table 1](#) and [Table 2](#). Denominator for the percentages will be the number of participants in the treatment group.

9. PHARMACOKINETIC (PK), BIOMARKER (NfL) AND PHARMACOGENOMIC ANALYSIS

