
 To evaluate the PK of pridopidine and its main metabolite in participants with HD 	
 Plasma concentrations of pridopidine and its main metabolite at Weeks 26, 52, 65, and 78 and at last participants' visit Relationship between plasma concentration of pridopidine and clinical outcome measures
Safety and Tolerability Endpoints	

 To evaluate the safety and tolerability of pridopidine in participants with HD 	
 Incidence (count and rate) of adverse events (AEs) and serious AEs (SAEs) overall, by severity, by relationship to study drug, and those that led to withdrawal from the study treatment or study Incidence and shifts of clinically significant abnormalities in electrocardiogram (ECG), laboratory tests, vital signs, and abnormalities in physical and neurological exam Analysis of Columbia-Suicide Severity Rating Scale (C-SSRS) throughout the study Tolerability: 
 The number (%) of participants who complete the treatment period The number (%) of participants who fail to complete the treatment period due to AEs The number (%) of participants who fail to complete the treatment period meeting the QTcF-change, Creatinine Clearance (CrCl) or Psychiatric Stopping Rules

Objectives and Endpoints of the Open-Label Extension (OLE) Period:

Objectives	Endpoints
Efficacy	

 To evaluate the long-term treatment effect of pridopidine in participants with HD who previously completed the Main Study 	
 Proportion of participants with change from Baseline (Main Study) to each OLE visit in UHDRS-TFC ≥ -1

- Proportion of participants with change from Baseline (Main Study) to each OLE visit in UHDRS-TFC ≥ 0
- Change from Baseline (Main Study) to OLE visits in
 - UHDRS-TFC
 - cUHDRS
 - UHDRS-TMS
 - Quantitative motor (Q-Motor):
 - [REDACTED]
 - [REDACTED]
 - [REDACTED]
 - SDMT
 - SWR
- Change from Baseline (Main Study) to OLE visits in:
 - CGI-C
 - PBA-s
 - HDQoL

Safety and Tolerability Endpoints

- To evaluate long-term safety and tolerability of pri dopidone in participants with HD who previously completed the Main Study
- Incidence (count and rate) of AEs and SAEs overall, by severity, by relationship to study drug, and those that led to withdrawal from the study treatment or study

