3. STUDY DESIGN

3.1. General Design and Study Schema

This is a multicenter, randomized, parallel group, double-blind, placebo-controlled study to evaluate the efficacy and safety of pridopidine administered orally at a dose of 45 mg bid versus placebo in treatment of functional impairment in participants with early HD, defined as Stages 1 and 2 based on UHDRS-TFC scores (HD1 is UHDRS-TFC 11-13 and HD2 is UHDRS-TFC 7-10). It is planned to enroll a total of 480 participants (240 participants within each treatment arm).

The study will consist of a screening period, a double-blind treatment period (hereafter referred to as the Main Study) and an OLE as described in study schemas [Figure 1](#)- Main Study and [Figure 2](#)- OLE.

After having signed an informed consent, each participant will be randomized in a 1:1 ratio to the active (pridopidine 45 mg bid) or control (placebo) arm, stratified by Baseline HD stage (HD1 vs. HD2) and Baseline neuroleptic use (Yes/No), for a 65 to 78 weeks double-blinded treatment period as the Main Study.

The Main Study will include an initial 2-week titration period, a 63-week double-blind full-dose maintenance treatment period, followed by a variable double-blind treatment period of up to 13 weeks.

Starting on Day 1, during the titration period, all participants will self-administer 1 capsule of study drug orally, once daily (QD), in the morning for 2 weeks. Thereafter, the study drug will be taken orally bid in the morning and in the afternoon (7-10 hours apart) for 63 weeks (full-dose maintenance double-blind treatment period). Participants who complete the Maintenance period (63 weeks) will continue into a variable double-blind period of up to 13 weeks or until the last participant randomized completes 65 weeks of treatment (2-weeks Titration + 63-weeks full-dose), whichever comes first.

The reason for the variable length double-blind period is because the study will be considered to have completed when the last participant randomized (and who has not discontinued) completes 65 weeks of double-blind treatment. Participants enrolled prior to that in the study will have the opportunity to complete 78 weeks in the Main Study. Participants enrolled towards the end of the study will have completed between 65 and 78 weeks in the Main Study. The primary endpoint is the change from Baseline to Week 65 in UHDRS-TFC. Change from Baseline to Week 52 and 78 in UHDRS-TFC are secondary endpoints, as indicated in the Section 2.

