5. GENERAL CONSIDERATIONS FOR DATA ANALYSES AND HANDLING

This section addresses the definitions, algorithms, imputations, and conventions that will apply to the analysis and handling of the data in general. Rules that are data specific will be addressed in the detailed discussions of individual sections below. This SAP and all Tables, Figures and Listings (TFLs) created will use U.S. spelling.

All changes to this SAP prior to locking the database and unblinding the study will be documented in an Addendum.

Any additional analyses performed or changes to the SAP and Addendums after unblinding the study will be described in the CSR under the section “Changes to Planned Analyses”.

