5.1. General Summary Tables, Figures and Individual Participant Data Listing Considerations

Summary tables and listings (e.g., post text tables and individual participant data listings) are prepared according to ICH Guideline E3 will include a “footer” providing explanatory notes that indicate as a minimum (1) Date and time of output generation; (2) SAS program name, including the path that generates the output; (3) Any other output specific details that require further elaboration; (4) Page number in the format of Page X of Y.

Summary tables will include reference(s) to the participant data listing(s) to support the summary data. The data extraction date links the output to the archived database that is frozen to ensure the replication of the results.

For the Main Study, summary tables will display the 2 treatment groups, “Placebo” and “Pridopidine 45 mg bid”. An overall total column will be included, where appropriate.

Unless specified, row entries in summary tables are always displayed for every category even if no data exists for any participants (e.g., a row with all zeros will appear). The summary tables will clearly indicate the number of participants to which the data apply along with an indication for the number of participants with missing data.

If no data exist for any participants for a given Table or Listing, a text will be displayed to indicate why there is no data.

In summary tables for medications, medical conditions and AE verbatim (reported) terms are coded to preferred terms (PT) and body/organ systems are coded per standard dictionaries mentioned in Section 5.3.

All relevant data collected in the study will be presented in individual Participant Data Listings (unless agreed to with the agency to not create certain listings, e.g., Laboratory listings, which tend to be very large). All listings will include participant ID and treatment group. Where applicable, listings will also include visit number, visit date, and days relative to the initiation of treatment. Individual participant data listings, at a minimum, are sorted by Treatment, Participant ID, Assessment and Visit (Week), as applicable.

Relevant data derived for analyses will also be included with the raw data in the listings.

Supporting figures may be generated for key tables.

5.2. General Post Text Summary Table and Individual Participant Data Listing Format Considerations

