5.4. Data Presentation Conventions

Continuous variables (e.g., age) are summarized using descriptive statistics (the number of participants with available data, the mean, SD, first quartile (Q1), median, third quartile (Q3), minimum and maximum). Categorical variables (e.g., race) are summarized using counts and percentages. Percentages are calculated using the total participants per treatment group with available data (overall or within relevant subgroup when appropriate). Summaries for discrete variables will include frequencies and percentages. Unless obvious, denominators used for computation of percentages will be indicated in footnotes on tables.

The following conventions will be applied to all data presentations and summaries.

- For continuous variables, all mean, Q1 (25th percentile), median and Q3 (75th percentile) values are formatted to one more decimal place than the measured value. SD values are formatted to two more decimal places than the measured value. Minimum and maximum values are presented with the same number of decimal places as the measured value. This rule may be modified to fit data in a given table as long as the data displays relevant decimal places for interpretation of results.
- For categorical variables, the number and percentage of responses are presented in the form XX (XX.X%) where the percentage is in the parentheses and will be rounded to one decimal place.
- Date variables are formatted as DDMMYYYY for presentation. Time is formatted in military time as HH:MM for presentation.
- Wherever possible, data will be decimal-centered, or left aligned as appropriate to best display the data and column headers. Parentheses will also be aligned appropriately for best display. This will be detailed in the mock shells.
- P-values, if applicable, will be presented to 4 decimal places. If the p-value is less than 0.001 then it will be presented as <0.001. If the rounded result is a value of 1.000, it will be displayed as >0.999.
- Summaries of clinically significant abnormal values will include all post-baseline values (including scheduled, unscheduled, and ET visits).
- Unless otherwise stated, any statistical tests performed will use 2-sided tests at the 5% significance level.

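### SAP 8.11 divides by-visit examination results by everyone in the treatment group, so each percentage is understated by the fraction not examined at that visit

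*SAP*

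**What the plan says.** SAP 8.11 states that examination results, graded normal or abnormal with further categories for some neurological items, "will be summarized using counts and percentages at visits described in" the two schedules of activities (SAP Table 1 for the Main Study, Table 2 for the OLE). It then fixes the base: "Denominator for the percentages will be the number of participants in the treatment group".

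SAP 5.4 sets a different general convention: "Percentages are calculated using the total participants per treatment group with available data". The introduction to SAP Section 5 makes such conventions open to refinement: "Rules that are data specific will be addressed in the detailed discussions of individual sections below". SAP 5.1 requires summary tables to give the number of participants to whom the data apply, "along with an indication for the number of participants with missing data". SAP 5.8.3 presents safety data as observed, without imputation.

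The outcome is a named one. The safety endpoints in SAP Section 2 include "abnormalities in physical and neurological exam", and SAP 3.2.7 lists both examinations again.

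**The concern.** An examination finding belongs to one visit. A participant who was not examined at that visit stays in the 8.11 denominator but cannot enter the numerator, so the percentage mixes two things: how often an abnormality was found, and how often anyone looked. A visit with more missing examinations shows a lower abnormality percentage even if the rate among those examined is unchanged. If the arms differ in the fraction examined, two arms with the same rate print different percentages.

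Some of this missingness is built into the design:

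- **Week 78.** SAP 3.1 says: "Participants enrolled towards the end of the study will have completed between 65 and 78 weeks in the Main Study". Under Table 1 footnote e, those whose Week 65 visit falls within 4 weeks of the last participant's finish at Week 65 and have no later Main Study visit.
- **Phone visits.** SAP Table 3 marks the full and the brief examination as not done at converted virtual visits. Protocol 7.2 lets participants who have stopped study drug replace clinic visits by phone, except at Week 65, Week 78/EoS and ET.
- **OLE.** SAP 3.1 has OLE treatment run until 12 months after the last participant completes double-blind treatment. Protocol 4.4 plans recruitment from Q3 2020 to about Q4 2021. SAP Table 2 schedules visits at OLE Week 52 and every 26 weeks after that. Follow-up is therefore staggered, and under this plan only earlier enrollees can reach the later OLE visits.

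**Working it through.** SAP 8.11 states no figure to reproduce. The nearest stated inputs are in SAP 3.3: 480 randomised, 22.5% dropout, 372 remaining. These agree: 480 × (1 − 0.225) = 372, or 186 of 240 per arm.

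**Formula.** Let N be the number in the treatment group, m the fraction not examined at the visit, and a the number with an abnormal result.

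- 8.11 percentage = a / N
- 5.4 percentage = a / [N(1 − m)]
- Ratio of 8.11 to 5.4 = 1 − m

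The relative understatement is therefore exactly m, whatever the abnormality rate or arm size. SAP version 3.0 records 499 randomised against the planned 480; this does not alter the ratio.

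**Inputs for m.** SAP 3.6.3.1 gives 98.9% completion of in-clinic UHDRS-TFC as of October 2022, so m = 1.1%. SAP 3.2 gives under 2% of scheduled in-clinic visits not performed or lacking UHDRS-TFC as of September 2022, so 2% is used as the upper value. SAP 3.3 gives the planned 22.5%. An assumed 40% stands for a visit with many examinations missing by design, because the number of late enrollees without a Week 78 visit is not given.

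**Abnormality rate.** The documents give none; 5%, 20% and 50% among those examined are assumed.

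| m | 5% prints as | 20% prints as | 50% prints as |
|---|---|---|---|
| 1.1% | 4.9% | 19.8% | 49.5% |
| 2% | 4.9% | 19.6% | 49.0% |
| 22.5% | 3.9% | 15.5% | 38.8% |
| 40% (assumed) | 3.0% | 12.0% | 30.0% |

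Worked case, N = 240 and m = 22.5%: 186 are examined, 0.20 × 186 = 37.2 are abnormal, and 37.2 / 240 = 15.5%.

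**Comparison between arms, 20% in both arms among those examined.**

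- Equal m of 22.5%: 15.5% against 15.5%. There is no false difference. A true difference would shrink by the factor 1 − m, and the ratio of rates would be unchanged.
- Assumed m of 25% active and 20% placebo: 0.20 × 0.75 = 15.0% against 0.20 × 0.80 = 16.0%, a false difference of 1 point.
- Assumed m of 30% active and 15% placebo: 0.20 × 0.70 = 14.0% against 0.20 × 0.85 = 17.0%, a false difference of 3 points.

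**The case against.** A reader might infer that the SAP contradicts itself. It does not, strictly. Section 5 leaves data-specific rules to later sections, and 5.4 expects denominators to vary, since it asks for them in table footnotes unless obvious. Full-group denominators appear elsewhere, in SAP 8.4 for adverse events and SAP 6.1 for disposition. What survives is that those are cumulative counts, with one outcome per participant over a period, and they do not justify the same base for a visit-specific finding. Neighbouring by-visit summaries allow for missing assessments: SAP 8.9 reports the number evaluated on the C-SSRS, and SAP 8.6 carries a missing category for laboratory values.

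A reader might also infer that unexamined participants are reported as normal. They are not. Every graded category shrinks by the same factor, and the missing count required by SAP 5.1 lets a careful reader recover the rate among those examined. This objection stands, and it limits the harm.

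A large fall at late visits is a third tempting inference. The documents do not show one. The only observed completion figures imply 1–2% missing, and SAP 3.6.3.1 cites a low discontinuation rate. Those figures concern UHDRS-TFC and not examinations, date from before the Main Study ended, may not count visits after withdrawal, and do not cover the OLE. Protocol 4.1 expects most participants to be followed for 78 weeks, and those more than 4 weeks past Week 65 still have an EoS visit. Nor are the visit columns one series: brief examinations fall at Weeks 4, 26 and 39 and full ones at Baseline and Weeks 52, 65 and 78, and Protocol 8.2.1 gives the two types different content.

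Finally, dividing by those examined conditions on retention and can itself be distorted by unequal dropout. That is true, and it is why the number not examined must be shown beside the percentage.

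**Conclusion.** The point holds as a reporting defect of limited reach. The relative understatement equals the missing fraction; that follows from the 8.11 rule and the absence of imputation, and needs no assumption. The size in percentage points rests on an assumed abnormality rate and on a missing fraction that the documents do not give for examinations.

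With a 20% rate, the loss is 0.2–0.4 points if the autumn 2022 completion figures carry over to examinations through Week 65, and 4.5 points at the planned 22.5% dropout. It can be larger at Week 78 and at later OLE visits.

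A false difference between arms is possible but not shown. Week 78 missingness in the last group follows enrolment date and should be balanced by randomisation. Phone visits after stopping study drug could differ by arm, but the documents report no such difference. These are descriptive safety tables, so no hypothesis test or efficacy conclusion depends on the choice.

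**What to change.** Replace the denominator sentence in SAP 8.11 with wording to this effect: *At each visit, percentages are calculated over those in the treatment group who had that examination at that visit.* Apply it to the Main Study and the OLE, and print the number not examined at each visit, as SAP 5.1 already requires. If the sponsor prefers to keep the full group as the base, 8.11 should give the reason and the table footnote should state the denominator.

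The cost is one sentence in the SAP and one change of denominator in the table program. No new data are needed.
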